23. TRAINING

[name], co-inventor of the device will train the investigators on the use of the SiteSeal™ device, trial protocol and record keeping in both classroom and lab environments. Each investigator will have 2roll-in placements before beginning the trial. The results of the roll-in patients will be collected, but not tabulated as part of the trial.

24. DISPERSION, STORAGE & RETURN OF DEVICE

Upon site receipt of device, an inventory must be performed and a device receipt form filled out and signed by the person accepting the shipment. The date the device was received, the number of devices received, the lot number of the device and the person who received device must be documented on a Site/Dispersion/Return Log. Any damaged device will be documented and the sponsor notified immediately.

25. STUDY OVERSIGHT

This study is evaluating an investigational device. The decision to stop the study will be made by the CEO, Chief Medical Officer for Woundcare360 LLC and the VP Quality and Regulatory Affairs.

26. STATISTICAL PLAN

Objective

The purpose of this study is to establish the safety of the SiteSeal™ Adjunctive Compression Device.

Study Design

The study design is a single arm with 90 enrolled patients, open-label, single center clinical trial.

Handling Missing Data

No imputation will be done for missing data.

Handling Dropouts

The numbers of patients who enter and complete the trial will be tabulated, and details concerning reasons for withdrawals will be listed.

Statistical Methods

Primary Safety Analyses

For the risk of each of the two primary safety endpoints, namely common femoral nerve puncture and common femoral artery laceration, percent of patients exhibiting the risk and its one-sided 95% upper confidence limit will be shown. We expect very low risk for the above two endpoints. In case that we observe no cases for each of the above endpoints, with 90 patients for the device group, we can claim that we are 95% confident that the risk is less than 3.3%.

Secondary Safety Analyses

For the risk of each of the major complications and minor complications, percent of patients exhibiting the risk and its two-sided 95% upper confidence interval will be shown. For the score of patient discomfort, the mean score and its 95% two-sided confidence interval will be reported.

Baseline Patient Characteristic Data

For each of quantitative baseline data such as age, height, BMI, and blood pressures, etc., the mean score and its 95% two-sided confidence interval will be reported.

For each of qualitative baseline data such as procedure type, presence or absence of peripheral vascular disease, and size of the introducer sheath, etc., its frequency distribution will be shown.

Populations for Analysis

All patients in this study are expected to receive the test device, and they will be categorized as intent-to-treat (ITT) patient population. All analyses will be conducted based on this ITT population.

The calculations will be performed using SAS® software for Windows¹, Version 9.4, Copyright (c) 2002-2012 by SAS Institute Inc., Cary, NC, USA.

References

1. SAS OnlineDoc Version Nine for the Web, SAS Institute Inc., Cary, NC, USA.
<http://support.sas.com/documentation/onlinedoc/sas9doc.html>

27. DATA MANAGEMENT

The data will be owned and maintained by Woundcare360 LLC. Woundcare360 LLC will analyze the data. This analysis may be provided to the FDA. A description of this clinical trial will be available on <http://ClinicalTrials.gov> as required by US Law. This website will not include information that can identify subjects. Subjects can search this website at any time. The data may be used for presentations and submitted to journals. All subject matter will remain confidential, and at no time will any subject names or other identifying data be used.

28. IRB REVIEW

The IRB for MOVI is:

Quorum Review IRB
[name]
[name]

The IRB Chairman is [name].

The protocol, informed consent document and relevant supporting information must be submitted to the IRB for review and must be approved before the study is initiated. In addition, any subject recruitment materials must be approved by the IRB prior to being used. This study will be conducted in accordance with the ethical principles that have their origin in the Declaration of Helsinki and that are consistent with Good Clinical Practice and applicable regulatory requirements. The study must be conducted in accordance with the regulations of the United States Food and Drug Administration (FDA) as described in 21CFR 50 and 56 and 812, applicable laws and the IRB requirements.

The sponsor must submit any change to the protocol to the IRB for review and approval before implementation. A protocol change intended to eliminate an apparent immediate hazard to subjects may be implemented immediately provided the FDA and the reviewing IRB are notified within 5 working days.

It is the responsibility of the investigator to provide each subject with full and adequate verbal and written information using the IRB approved informed consent document, including the objective and procedures of the study and the possible risks involved before inclusion in the study. Informed consent must be obtained prior to performing any study-related procedures, including screening and changes in medications, including any washout of medications. A copy of the informed consent must be given to the study subject.

**Statistical Analysis Plan:**

**Document Date: November24, 2015**

## **STATISTICAL PLAN**

### **Objective**

The purpose of this study is to establish the safety of SiteSeal™ Adjunctive Compression Device.

### **Study Design**

The study design is a single arm with 90 enrolled patients, open-label, single center clinical trial.

### **Handling Missing Data**

No imputation will be done for missing data.

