18. METHODS / STUDY DESIGN

Institutional Review Board (IRB) approval will first be obtained. A subject's participation is a one-time event (plus follow-up) that occurs after obtaining informed consent. The subjects will not incur any costs associated with the study procedures.

At the catheter lab site, subjects will be screened through a standard of care history. After determining that the patient qualifies for enrollment into the study, an investigator or delegated study personnel will obtain an informed consent. After the patient's informed consent is obtained, study personnel will interview the subject and document subject data, including their age, gender, race, and patient history into their file. The subject source data is then recorded on a sponsor-provided Case Report Form (CRF).

Each subject will undergo the doctor-determined interventional procedure before closing with SiteSeal™.

The first 50 patients will receive a pre-device deployment ultrasound of the access site on the day of catheterization and a post-procedure ultrasound (after device removal and no later than the 30day follow-up) to detect silent complications, including vascular injury requiring repair, pseudoaneurysms requiring thrombin or fibrin adhesive injections, or bleeding requiring transfusions.

All patients will return for a follow-up visit at 30 days (± 1 week) post-procedure. A physician investigator (i.e. principal investigator, sub-investigators, physician assistants and/or nurse practitioners associated with the investigators) will examine the femoral artery access site. Any access site-related complications will be reported to the PI.

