22. MONITORING PROTOCOL

II. Monitors

- a. [name]
 - i. CEO
 - ii. [contact]
 - iii. [contact]

CEO/President: In-Vitro Medical Diagnostics career with more than thirty-five years of progressive professional experience in management, that included the reorganizing and streamlining of all departments in both the Medical Laboratory and Medical Device space with FDA, PMA, and CLIA oversight that resulted in bringing new products to market and the establishment of international distributors that resulted in 45% of total sales.

[name] was responsible for the overall management of all aspects of Primus Diagnostics, a medical diagnostic company.

[name] co-developed the protocol, the investigational device, the written informed consent form and all documents provided to subjects, applicable regulators and to the Principal Investigators.

- b. [name] [contact] [contact]
[name] Vitae is in the IDE CV Section.

III. Purpose

- a. To verify that the rights and wellbeing of human subjects are protected.
- b. The reported trial data are accurate, complete and verifiable from source documents.
- c. The conduct of the trial is in compliance with the currently approved protocol, with GCP and with the applicable regulatory requirements.

IV. Extent and Nature of Monitoring

- a. The Monitor is the main line of communication from the Sponsor to the PI

V. Monitoring site visit (biweekly)

VI. Monitoring report

- a. The monitor will submit a written report to file after each trial-site visit or trial communication with the PI.
- b. Reports will include the date, site, name of the investigator or other individual contacted.
- c. Reports will include a summary of what was reviewed and the findings/facts, deviations and deficiencies, conclusions, actions taken and/or actions recommended to secure compliance.
- d. In the event of a non-compliant investigator, the deficiency will be pointed out, documented and corrective action initiated.
- e. In the event of repeated non-compliance, the investigator will be dropped from the trial
- f. Data from an incomplete CRF will not be used in the statistical analysis.

Sponsor: Woundcare 360 LLC

Project: Clinical Study of SiteSeal following Diagnostic and Interventional Cardiovascular Procedures

Date of Site visit:

Monitor Name

Monitor Signature

DATE

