### **Handling Dropouts**

The numbers of patients who enter and complete the trial will be tabulated, and details concerning reasons for withdrawals will be listed.

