### **Populations for Analysis**

All patients in this study are expected to receive the test device, and they will be categorized as intent-to-treat (ITT) patient population. All analyses will be conducted based on this ITT population.

The calculations will be performed using SAS® software for Windows, Version 9.4, Copyright (c) 2002-2012 by SAS Institute Inc., Cary, NC, USA.

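### Once a 30-day visit is missed, the rules on imputation, ITT and incomplete CRFs conflict, and no denominator is set for the 30-day complication rates

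*SAP*

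**What the plan says.** - **Missing data** (SAP, Handling Missing Data; same rule in Protocol section 26): "No imputation will be done for missing data".
- **Population** (SAP, Populations for Analysis): "All patients in this study are expected to receive the test device, and they will be categorized as intent-to-treat (ITT) patient population". Then: "All analyses will be conducted based on this ITT population".
- **Size** (SAP, Study Design): "The study design is a single arm with 90 enrolled patients, open-label, single center clinical trial".
- **Dropouts** (SAP, Handling Dropouts): "The numbers of patients who enter and complete the trial will be tabulated, and details concerning reasons for withdrawals will be listed". Neither document gives an expected dropout rate, and neither plans a sensitivity analysis.
- **Follow-up** (Protocol section 18): "All patients will return for a follow-up visit at 30 days (± 1 week) post-procedure". Protocol section 19 takes the major and minor complications from this visit.
- **Estimator** (SAP, Secondary Safety Analyses): each complication is reported as a percentage of patients with a 95% interval. The denominator is not stated for patients who have no visit.
- **Incomplete forms** (Protocol section 22): "Data from an incomplete CRF will not be used in the statistical analysis". The SAP does not repeat this rule.

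**The concern.** A percentage needs a denominator, and for the 30-day complications the plan points to more than one. If a patient does not return, keeping that patient in the ITT denominator without an event assigns an outcome nobody observed, which is a single imputation of no complication. Leaving the patient out respects the ban on imputation, but then the analysis covers available cases and not the whole ITT population. The incomplete-CRF rule goes further: read literally, it removes what was recorded for a patient whose form is unfinished, including a complication noted before the patient was lost.

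The study's stated purpose is to establish safety, in one arm, with events expected to be rare. There is no control group in which the same missing-data error might partly cancel. In that setting a handful of unassessed patients can outnumber the observed events. If the denominator is settled only after the data are in, it can be chosen with the result in view.

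**Working it through.** **1. Inputs.** N = 90, the ITT rule and the no-imputation rule come from the SAP. The 30-day visit and the CRF rule come from Protocol sections 18, 19 and 22. The number missing is an assumption; 2 to 18 of 90 (about 2% to 20%) is shown. The interval method is not named, so exact (Clopper-Pearson) limits are assumed. The SAP's wording for the secondary interval is read as an ordinary two-sided 95% interval.

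**2. The plan's own figure.** For 0 events in n patients the exact one-sided 95% upper limit is 1 − 0.05^(1/n). With n = 90 this is 3.27%; the rule of three gives 3/90 = 3.33%. Both agree with the stated 3.3%.

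**3. Three ways to handle missed visits, with no observed events.** The two-sided 95% upper limit at 0/n is 1 − 0.025^(1/n). For x > 0 it is the p that solves P(X ≤ x | n, p) = 0.025.

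| Missing (assumed) | Counted event-free | Dropped | All counted as events (bound) |
|---|---|---|---|
| 2 | 0/90: 4.02% | 0/88: 4.11% | 2/90 = 2.2%, limit 7.80% |
| 5 | 0/90: 4.02% | 0/85: 4.25% | 5/90 = 5.6%, limit 12.49% |
| 9 | 0/90: 4.02% | 0/81: 4.45% | 9/90 = 10.0%, limit 18.14% |
| 18 | 0/90: 4.02% | 0/72: 4.99% | 18/90 = 20.0%, limit 29.75% |

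With 2 observed events and 9 missing, the results are 2/90 = 2.22% (0.27 to 7.80%), 2/81 = 2.47% (0.30 to 8.64%), and a worst case of 11/90 = 12.22% (upper limit 20.82%).

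**4. Direction of the bias.** Let d be the fraction missing, p1 the risk in patients seen and p0 the risk in patients not seen. The true risk is (1 − d)p1 + d·p0.

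- Counted event-free: the estimate is (1 − d)p1 and the bias is −d·p0, which is never positive.
- Dropped: the estimate is p1 and the bias is d(p1 − p0), which is negative only if p0 > p1.

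With d = 10% and p1 = 3% (both assumed), event-free counting estimates 2.7% and dropping estimates 3.0%:

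| p0 | True risk | Bias, event-free | Bias, dropped |
|---|---|---|---|
| 0% | 2.7% | 0 | +0.3 points |
| 3% | 3.0% | −0.3 points | 0 |
| 10% | 3.7% | −1.0 points | −0.7 points |

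**5. The CRF rule.** Suppose the only complication in the study occurs in a patient whose CRF is later left incomplete. If it is kept, the result is 1/90 = 1.11% (upper limit 6.04%). If it is discarded with the form, the result is 0/89, with upper limit 1 − 0.025^(1/89) = 4.06%. An observed event has disappeared.

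**6. Reach into the primary endpoints.** Protocol section 19 defines the nerve endpoint by what happens when the device is placed, so a missed 30-day visit does not touch it. Excluding incomplete CRFs could still shrink its denominator, but only slightly: 0/88 gives 1 − 0.05^(1/88) = 3.35%, against 3.27% at 0/90.

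**The case against.** The case on the other side has substance. The ITT sentence says who belongs to the population, and the no-imputation sentence says that values will not be filled in. With complete follow-up, or with observed outcomes reported alongside their n, both can be honoured. The natural meaning of no imputation is an available-case analysis; nowhere does the plan say that absent patients count as event-free. Eligibility selects for follow-up (inclusion criterion 4, exclusion criteria 5 and 35). The complication rates are descriptive, with no performance goal to pass or fail. The worst case is an extreme.

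Most of this stands, and it limits the point. It does not remove it. The available-case reading is plausible but unwritten, and it departs from the sentence that puts all analyses on the ITT population. The SAP is the later document and omits the CRF rule, but neither document as available says which prevails.

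Four stronger readings are tempting, and the documents do not support them:

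- *Either handling favours the device.* Only event-free counting always does so or is neutral. Dropping is unbiased when missingness is unrelated to outcome, can overstate the risk, and for the same event count gives the higher limit (4.25% against 4.02%).
- *The two SAP rules can never both hold.* The conflict is conditional on a missed assessment.
- *Patients would vanish silently.* Completers are to be counted and withdrawal reasons listed. What is missing is how non-completers enter the percentages.
- *Patients with complications are the ones who will not return.* This is possible, but nothing in the documents shows it.

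**Conclusion.** The point holds as a conditional conflict and a gap in specification. If every patient has a 30-day assessment and a complete CRF, it has no effect. If any visit is missed, the plan does not determine the 30-day complication rates, and one of the possible calculations can only err towards lower risk. The CRF rule is the sharpest textual conflict, because it can remove an event that was actually seen.

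The gap between the two plausible denominators is small: 4.02% against 4.25% with 5 missing and no events. The uncertainty that goes unreported without a sensitivity analysis is larger, up to 12.5% in the same example. That last figure is a bound and not an estimate of bias. All sizes rest on assumed missing counts and exact limits.

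A reader might infer that the 3.3% statement for the primary endpoints is undermined. It is not: it does not rest on the 30-day visit, and losing two CRFs would move it by less than 0.1 percentage points. The plan should be amended on this point, but the matter is mainly one of secondary safety reporting.

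**What to change.** 1. **Denominator.** In Protocol section 26 and in the SAP sections on missing data and analysis populations, state that 30-day complication rates use ITT patients who have a 30-day assessment, or an event recorded before it. Show n and the number not assessed beside each rate.
2. **Recorded events.** Amend the CRF rule in Protocol section 22 so that recorded events stay in the analysis even when the CRF is incomplete. Without this change, the new denominator rule would still be contradicted.
3. **Sensitivity.** Add one table in which every treated patient without a 30-day assessment counts as having the complication, labelled as a worst-case bound. A tipping-point version would also serve.
4. **Primary endpoints.** If the placement record needed for a primary endpoint is missing, count that patient as having that primary event in the sensitivity analysis.

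The cost is a few sentences in two documents and one extra table, with no new data collection. If there are dropouts, the sensitivity figure will look less favourable than the main one. The change should be made before outcomes are reviewed.

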### **Handling Dropouts**

The numbers of patients who enter and complete the trial will be tabulated, and details concerning reasons for withdrawals will be listed.

### **Statistical Methods**

#### **Primary Safety Analyses**

For the risk of each of the two primary safety endpoints, namely common femoral nerve puncture and common femoral artery laceration, percent of patients exhibits the risk and its one-sided 95% upper confidence limit will be shown. We expect very low risk for the above two endpoints. In case that we observe no cases for each of the above endpoints, with 90 patients for the device group, we can claim that we are 95% confidence that the risk is less than 3.3%.

#### **Secondary Safety Analyses**

For the risk of each of the major complications and minor complications, percent of patients exhibits the risk and its two-sided 95% upper confidence interval will be shown. For the score of patient discomfort, the mean score and its 95% two-sided confidence interval will be reported.

#### **Baseline Patient Characteristic Data**

For each of quantitative baseline data such as age, height, BMI, and blood pressures, etc., the mean score and its 95% two-sided confidence interval will be reported.

For each of qualitative baseline data such as procedure type, presence or absence of peripheral vascular disease, and size of the introducer sheath, etc., its frequency distribution will be shown.

### **Populations for Analysis**

All patients in this study are expected to receive the test device, and they will be categorized as intent-to-treat (ITT) patient population. All analyses will be conducted based on this ITT population.

The calculations will be performed using SAS® software for Windows, Version 9.4, Copyright (c) 2002-2012 by SAS Institute Inc., Cary, NC, USA.

